#### 8.2.8 Pulmonary Lung Function Tests

Evaluation of pulmonary lung function will only be required during screening for eligible participants with pre-existing obstructive or fibrotic lung conditions. Testing will be done locally according to the recommendation of the Official Statement of the European Respiratory Society and American Thoracic Society [Miller et al, 2005].

Forced Expiratory Volume in the 1st second will be assessed at screening under medical supervision from a FVC maneuver. The highest value from 3 technically satisfactory attempts will be recorded (irrespective of the curve they come from). The chosen value should not exceed the next one by more than 150 mL. If the difference is larger, up to 8 measurements will be made and the largest value be reported. The ratio FEV/FVC will be derived from these highest values of each parameter. The FEV1 should be greater than 50% of predicted value or for FEV/FVC ratio, the fifth percentile LLN. Lung function measurements will be done with patients either standing or sitting with the nose clipped after at least 10 minutes rest.
All sites will use local equipment and local spirometry lab will be used.

### 8.3 Adverse Events and Serious Adverse Events

The Principal Investigator is responsible for ensuring that all staff involved in the study are familiar with the content of this section.

The definitions of an AE or SAE can be found in Appendix D.

Adverse events will be reported by the participant (or, when appropriate, by a caregiver, surrogate, or the participant's legally authorized representative).

The Investigator and any designees are responsible for detecting, documenting, and recording events that meet the definition of an AE.

#### 8.3.1 Time Period and Frequency for Collecting AE and SAE Information

Adverse events will be collected from time of signature of ICF throughout the treatment period and including the follow-up period until 90 days after the last dose of study intervention.

Serious AEs will be collected from the time of signing of ICF until the end of the study.

If the Investigator becomes aware of an SAE with a suspected causal relationship to the study intervention that occurs after the end of the clinical study in a participant treated by him or her, the Investigator shall, without undue delay, report the SAE to AstraZeneca.

Adverse event and SAE collection will be performed per specified timelines regardless of whether the participant has initiated a new anticancer treatment. See Section 6.9 for reporting of AEs and SAEs during PTAP.

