Left ventricular ejection fraction by echocardiogram/ multiple-gated acquisition scan (Section 8.2.5) d		Х	If clinically indicated.			
Vital signs including pulse oximetry (Section 8.2.3)		Х	Х	Х		
Eastern Cooperative Oncology Group performance status (Section 8.2.6)		Х	Х	Х		
Assessment of B-Symptoms (Section 8.1.1)		X	Х	Х		
Assessment of AEs/SAEs (Section 8.3)		←	XX	→		
Concomitant medications (Section 6.5)		←→				
Subsequent anticancer therapy	Х	X	Х	Х	X	
Survival status (by telephone, email, or clinic visit)	Х	X	X	Х	X	
Disease status post HSCT if applicable (by telephone, email, or clinic visit) e					Х	
Blood and Urine Tests		·			·	
Clinical Chemistry (Section 8.2.7)		Х	Х	Х		
Hematology (Section 8.2.7)		Х	Х	Х		
Glycated hemoglobin (Section 8.2.7)		Х		Х		
Thyroid function (thyroid-stimulating hormone, free thyroxine, and free triiodothyronine as indicated f ; Section 8.2.7)		Х	x	Х		
Anti-thyroid antibodies (anti-thyroid peroxidase antibodies, thyroglobulin antibodies, thyrotropin receptor antibodies; Section 8.2.7)		Х	X	Х		
Hepatitis B and C virology (Section 8.2.7) g			Х			

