# 6.9 Continued Access to Study Intervention After the End of the Study

AstraZeneca will continue to supply sabestomig in the continued access phase of the study (ie, PTAP), if the participant consents to this, and while in the opinion of the investigator and in agreement with the medical monitor, the participant is benefiting from the treatment.

Treatment will continue until PD occurs as judged by the investigator, completion of a participant's current 35-cycle treatment period, or until meeting any other discontinuation criteria defined in Section 7.1. Participants should be followed according to the institution's SoC assessments and as deemed appropriate by the investigators. It is recommended that investigators continue to observe ongoing participants at the frequency employed prior to the final DCO. No further data collection is required, except for safety reporting. The investigator and any designees are responsible for detecting, documenting, and recording events that meet the definition of AE and SAE and special situations (see Sections 8.3, 8.4, and Appendix D). Adverse events will be collected from time of signature of ICF throughout the PTAP until 90 days after the last dose of sabestomig, regardless of whether the participant has initiated a new anticancer treatment.

Protocol dose modification and stopping criteria are to be followed while a participant is receiving sabestomig. A change in the dose/schedule of sabestomig should only occur for safety reasons, based on the investigator's judgment, and should follow the approach for dose reduction and discontinuation as described in this protocol.

In the event that product development reaches a point where alternative product supply options become available, then these alternative product supply options will be discussed by AstraZeneca with the investigator. AstraZeneca will work with the investigator to transition the participant(s) to alternative supply, where possible. In the event that AstraZeneca terminates further development of the study intervention, AstraZeneca will continue to supply study intervention where possible, however the supply may become unavailable. AstraZeneca will notify investigators in advance if supply of study intervention must be discontinued.

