## 7. DISCONTINUATION OF STUDY INTERVENTION AND PARTICIPANT DISCONTINUATION/WITHDRAWAL

## 7.1 Discontinuation of Study Intervention

It may be necessary for a participant to permanently discontinue (definitive discontinuation) study drug. Note that discontinuation from study drug is NOT the same thing as discontinuation from the study.

Participants may be discontinued from study drug in the following situations:

- Confirmed disease progression by PET-CT.
- An AE that meets criteria for discontinuation of study drug (as defined in Sections 6.6.3 and 6.6.8 and the Toxicity Management Guidelines, Appendix I) or in the opinion of the Investigator or AstraZeneca warrants discontinuation of further dosing.
- Investigator determination that the participant is no longer benefiting from study intervention.
- Participant decision. The participant is at any time free to discontinue treatment, without prejudice to further treatment.
- Pregnancy or intent to become pregnant (Section 8.3.10).
- Non-compliance with the CSP (Investigator or participant).
- Participant incorrectly initiated on study intervention.
  - When the reason does not impact safety consider the risk/benefit to the participant of stopping treatment.
- Unexpected, significant, or unacceptable risk to the participants enrolled in the study.
- AstraZeneca termination of study for reasons including but not limited to unfavorable risk/benefit or change in drug development plan.

If study drug is permanently discontinued, the participant will remain on study to be evaluated for protocol-specified assessments including follow-up of any AEs and survival follow-up. At the time of study drug discontinuation, the participant will be followed-up for safety and a visit will be performed 30 and 90 days after receiving the last dose of sabestomig.

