#### Participants discontinuing study treatment while in response (PR/CR) or with SD:

Participants will enter the safety follow-up and will carry on with efficacy assessments by imaging until PD, start of a new anti-cHL therapy or EoS, whichever comes first (Table 4 and Table 16).

Note:

- Radiotherapy administered alone after the last dose of sabestomig while a participant is in CR, with a consolidation intent will not be considered as a new anti-cHL line of therapy. Therefore, the participant should carry on the efficacy follow-up and perform disease assessment by imaging as per SoA (Table 16).
- Participant in CR/PR who proceeds to HSCT without any treatment between the last dose of sabestomig and the start of the conditioning regimen will be followed-up for disease assessment post-transplant as per SoC and data on their disease status will be collected in the EDC as part of the survival follow-up.

See the SoA (Table 1, Table 2, Table 3, and Table 4) for data to be collected at the time of discontinuation of study intervention and follow-up and for any further evaluations that need to be completed.

If the participant does not agree to continue in-person study visits, a modified follow-up must be arranged to ensure the collection of endpoints and safety information. This could be a telephone contact with the participant, a contact with a relative or treating physician, or information from medical records. The approach taken should be recorded in the medical records. A participant who agrees to modified follow-up is not considered to have withdrawn consent or to have withdrawn from the study.

All participants in Safety or Survival follow-up at the time of final study DCO will be contacted by the study site prior to the final study DCO to confirm their survival status and to inform participants that this was the last study-related contact, and no further survival data will be collected in respect to the study. Sites are requested to document this last contact in the source records.

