# 8.3.12 Deaths

All deaths that occur during the study intervention period, or within the protocol-defined follow-up period after the administration of the last dose of study intervention, must be reported as follows:

- Death clearly resulting from disease progression should be reported to the Study Monitor/Physician at the next monitoring visit and should be documented in the eCRF. It should not be reported as an SAE.
- Where death is not due (or not clearly due) to progression of the disease under study, the AE causing the death must be reported as an SAE within 24 hours. It should also be documented in the eCRF. The report should contain a comment regarding the coinvolvement of PD, if appropriate, and should assign main and contributory causes of death.
- Death with an unknown cause should always be reported as an SAE. It should also be documented in the eCRF. A postmortem may be helpful in the assessment of the cause of death, and if performed, a copy of the postmortem results should be forwarded to AstraZeneca Patient Safety or its representative within the usual time frames.

Deaths occurring after the protocol-defined safety follow-up period (90 days after the administration of the last dose of study intervention) should be documented in the eCRF. If the death occurred as a result of an event that started after the defined safety follow-up period and the event is considered to be due to a late-onset toxicity to study intervention, then it should also be reported as an SAE.

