4.5.2.2 Presentation

All TEAEs will be summarized and listed. AEs which are not treatment emergent will only be listed based on safety analysis set.

TEAEs will be counted once for each participant for calculating percentages of participants experiencing TEAEs. In addition, if the same TEAE occurs multiple times within a particular participant, the highest severity and level of relationship observed will be reported. For tables by MedDRA system organ class (SOC) and MedDRA preferred term (PT), participants with multiple TEAEs will be counted once for each SOC/PT.

An overall summary table of the number of participants experiencing each category of AEs will be produced. The number of participants experiencing TEAEs by MedDRA SOC and PT will be summarized and the type of incidence, severity, and relationship to IP will be summarized. Further splits by CTCAE grade, causal relationship to IP and AEs with Grade 3 or higher will also be also summarized.

Separate tables will present dose limiting toxicities, AEs leading to discontinuation, SAEs, IP-related adverse events

Details of any deaths will be summarized and listed. AEs leading to death are also summarized

SAEs

SAEs will be summarized as described above for the TEAEs.

AEs of special interest

Grouped summary tables of certain MedDRA PTs will be produced and may also show the individual PTs which constitute each AESI grouping. Groupings will be based on PTs provided by the medical team prior to database lock, and a listing of the PTs in each grouping will be provided.

Summaries of the above-mentioned grouped AE categories include number and percentage (%) of participants who have:

- At least one AESI presented by event outcome
- At least one AESI causally related to IP

At least one AESI leading to discontinuation of study intervention

A summary of total duration (days) of AESI will be provided for events which have an end date, and this may be supported by summaries of ongoing AESIs at death and, separately, at data cut-off.

ImAEs

ImAEs will be summarized as described above for the TEAEs.

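### SAE collection runs to the end of the study in Protocol 8.3.1, but nothing scheduled after Day 90 carries it out, 8.3.12 differs for late deaths, and the final-contact wording is not reconciled with the 90-day AE window

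*Protocol*

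**What the plan says.** Protocol 8.3.1 sets two periods. Non-serious AEs are collected from consent, "including the follow-up period until 90 days after the last dose of study intervention". For serious events the rule is longer: "Serious AEs will be collected from the time of signing of ICF until the end of the study". Both apply whether or not a new anticancer treatment has begun.

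Table 4 (Section 1.3) schedules the combined AE/SAE assessment from end of treatment through Day 30 to Day 90, as the row extracts. The six-monthly survival column asks for survival status, subsequent anticancer therapy and, where applicable, disease status after transplant. It has no AE or SAE entry.

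Protocol 8.3.12 has its own rule for deaths more than 90 days after the last dose. They are documented in the eCRF, and the SAE instruction is conditional: "If the death occurred as a result of an event that started after the defined safety follow-up period and the event is considered" to be late-onset toxicity of the study drug.

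On follow-up after stopping treatment, Section 7.1 says that "a visit will be performed 30 and 90 days after receiving the last dose of sabestomig". It also says, as does Table 4 footnote c, that "All participants in Safety or Survival follow-up at the time of final study DCO will be contacted by the study site" before that cut-off. Participants are told that the study will not contact them again and that survival data collection stops. Participants who move to the post-trial access programme (PTAP) are treated explicitly in Section 6.9: AE collection continues "throughout the PTAP until 90 days after the last dose of sabestomig".

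In the SAP (4.5.2.2), "SAEs will be summarized as described above for the TEAEs", and treatment-emergent means up to 90 days after the last dose and before subsequent cancer therapy.

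**The concern.** A site that works from the schedule will stop asking about SAEs at Day 90. A site that works from 8.3.1 will go on. Section 8 calls adherence to the schedule of activities essential, so neither site is careless. Completeness of SAE data after Day 90 would then vary by site for reasons unrelated to the drug. With a checkpoint inhibitor, late immune-mediated events are part of what the safety follow-up is there to find.

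For late deaths, the same event may be filed as a fatal SAE at one site and as a plain death record at another.

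The final-contact wording raises a separate question. Recent discontinuers, including those who stopped for toxicity, are the people for whom the 90-day window matters most. The text gives them a last contact without saying what happens to the rest of that window, while PTAP participants have an explicit safeguard.

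**Working it through.** No figure in the plan needs reproducing. The check is a comparison of passages, with two small illustrations.

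**Step 1. The SAE rule against the schedule.**
- 8.3.1: SAEs to the end of the study. 8.3.9: all SAEs are reported, related or not. 4.4: the study ends with the last participant's last visit or last Table 4 procedure.
- Table 4: the AE/SAE row ends at Day 90 and the survival column is blank for it.
- Result: between Day 90 and study end, 8.3.1 requires collection that no scheduled procedure performs.

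Illustration, on assumed dates: a participant receives a single dose and the study ends 6 months (about 183 days) later, in line with the earliest scheduled final-analysis timing in Protocol 9.4.1. The unscheduled period is 183 − 90 = 93 days. It is zero for anyone whose last dose falls within 90 days of study end, and longer for those who stopped earlier or if the study runs on.

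**Step 2. Late events under each rule.** Take events after Day 90 with the study still open.
- Non-fatal SAE (say at Day 150): required by 8.3.1; not asked about under Table 4; 8.3.12 is silent because it concerns deaths.
- Death unrelated to lymphoma and not judged drug toxicity: an SAE under 8.3.1 and Appendix D 2, which covers follow-up and counts death as a seriousness criterion; under 8.3.12, an eCRF record with no SAE instruction.
- Death from an event that began before Day 90: within 8.3.1; the late-death paragraph of 8.3.12 gives no SAE instruction.
- Death from an event that began after Day 90 and is judged late toxicity: an SAE under both. No conflict.

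The 8.3.12 conflict is therefore confined to fatal, non-progression events after Day 90.

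**Step 3. The final cut-off.**
- 7.1 requires Day 30 and Day 90 visits; 8.3.1 requires AEs to 90 days.
- 7.1 and footnote c give anyone in safety follow-up a final contact before the cut-off. They expressly end survival data only.
- SAP Section 1 sets the final cut-off when the last subject completes the last study visit. If that visit includes Day 90, nobody is cut short.
- SAP 3.1 sets it when the last participant has moved to PTAP. That trigger does not wait for anyone's Day 90.

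If collection did stop at a last contact t days after the last dose, uncovered AE days would be 90 − t:
- t = 21: 69 days (77%)
- t = 30: 60 days (67%)
- t = 60: 30 days (33%)
- t = 90: none

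These values of t are assumptions. The documents do not say how many participants would be in this position.

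**Step 4. What reaches the outputs.** Post-Day-90 SAEs are not treatment-emergent, so they are listed and not tabulated (SAP 4.5.2.2). Deaths are tabulated in SAP 4.5.3 without a 90-day limit, including AEs with fatal outcome more than 30 days after the last dose and a category for other deaths. A late non-progression death could land in either category, depending on whether the site followed 8.3.1 or 8.3.12.

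**The case against.** The strongest reply is that the general rules already govern. 8.3.1 and 8.3.9 require all SAEs, the SAE definition covers follow-up, and 8.3.12 never says that its late-toxicity case is the only one. Suspected related SAEs must be reported even after study end, and unresolved AEs are followed as medically indicated (8.3.2). Participants who stop in response or with stable disease also continue imaging, so the survival contact is not their only contact. All of this is true, but none of it puts an SAE question into the schedule after Day 90 or makes 8.3.12 agree with 8.3.1.

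Four stronger readings are tempting and are not supported:
- That 8.3.12 limits SAEs in general to late toxicity. It addresses deaths only.
- That participants at the final cut-off lose their 90-day window. The text stops survival data only, and 8.3.1 and 7.1 still require 90 days. Loss is an inference, and under SAP Section 1 it need not occur.
- That anyone dosed in the 90 days before the cut-off is affected. PTAP participants keep their window under 6.9.
- That differing collection after Day 90 distorts the primary safety incidences. The tables count treatment-emergent events, so later SAEs cannot change them, and late deaths are tabulated separately. Only actual loss of days inside the 90-day window could affect the tables.

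One caveat also stands: the span of the Table 4 arrow is read from extracted text. Its position points to Day 90, but the sponsor should confirm it against the original.

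**Conclusion.** The protocol is inconsistent as written on SAE collection after Day 90: 8.3.1 requires it, Table 4 does not schedule it, and 8.3.12 departs from it for fatal non-progression events. This rests on the texts, with the Table 4 arrow as extracted.

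The final-contact wording is a separate, weaker point: it is unreconciled with the 90-day AE rule, and whether it costs any data depends on which SAP cut-off statement applies.

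The size in participants or events cannot be stated. The gap is one of follow-up time, from Day 90 to study end, and the day counts above are illustrations on assumed dates. The consequence is uneven completeness of required safety data and inconsistent classification of late deaths, not a demonstrated bias in the primary safety tables. It is worth correcting because correction is cheap.

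**What to change.** Reconcile 8.3.1, Table 4 and 8.3.12 into one SAE collection rule. If 8.3.1 stands, add an SAE check to the existing six-monthly survival contact and align the late-death paragraph of 8.3.12 with it. The version history (Appendix L, Version 3) records that the end-of-study wording was introduced at an ethics committee's request, which the sponsor should weigh in choosing.

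In 7.1 and Table 4 footnote c, either confine the final-contact statement to survival follow-up, or state that participants within 90 days of their last dose complete AE/SAE collection to Day 90. Reconcile the cut-off statements in SAP Section 1 and SAP 3.1 so that it is clear whether the cut-off waits for those visits.

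Cost: protocol wording, one entry in Table 4, one question at contacts already made, and a SAP clarification. The downside is that safety reporting may stay open for up to about 3 months for a few recent discontinuers. A SAP table of SAEs with onset after Day 90 would be a useful option but is not needed, since those events are listed and deaths are already tabulated.

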#### 8.3.2 Follow-up of AEs and SAEs

Any AEs that are unresolved at the participant's last AE assessment in the study are followed up by the Investigator for as long as medically indicated, but without further recording in the eCRF. AstraZeneca retains the right to request additional information for any participant with ongoing AE(s)/SAE(s) at the end of the study, if judged necessary.

#### Adverse Event Variables

The following variables will be collected for each AE:

- Adverse Event (verbatim),
- The date and time when the AE started and stopped,
- NCI CTCAE v.5.0 grade and grade changes, with the date of change,

- Whether the AE is serious or not,
- Investigator causality rating against the Investigational product(s) (yes or no),
- Action taken with regard to investigational product(s),
- Adverse Event caused participant's withdrawal from study (yes or no), and
- Outcome.

In addition, the following variables will be collected for SAEs:

- Date AE met criteria for SAE,
- Date Investigator became aware of SAE,
- Seriousness criteria,
- Date of hospitalization,
- Date of discharge,
- Probable cause of death,
- Date of death,
- Autopsy performed,
- Causality assessment in relation to study procedure(s), and
- Causality assessment to other medication.

